6.2.1.2 Vineland Adaptive Behavior Scale, 3rd Edition

The VABS-3 is a standardized psychometric instrument designed to measure personal and social skills needed for everyday living (Sparrow et al 2005; Sparrow et al 2016). The VABS-3 is administered via a caregiver using a semi-structured interview format and assesses 4 main

adaptive domains: communication (receptive, expressive and written), socialization (interpersonal relationships, play and leisure, coping skills), daily living skills (personal, domestic, community), and motor skills (fine and gross). It also includes a maladaptive behavior scale for identifying behavior problems in children through 18 years of age. The scale has been found to have good internal consistency, test-retest reliability and validity (Sparrow et al 2016). The VABS-3 interview form will be used to evaluate subjects on the communication, socialization, daily living skills, motor skills and maladaptive behavior domains to assess their overall functioning. This assessment is an interview of the caregiver by a trained qualified rater, and for each study site, the same rater is to be used throughout the study. As an exception, another Sponsor-trained qualified rater in VABS-3 may be used.

6.4 Safety Assessments

Safety assessments will include frequency, severity, and causality of AEs (including SAEs and AEs leading to study discontinuation), and other safety assessments including assessment of suicidality, collection of seizure diaries, clinical laboratory assessments, vital sign measurements, and physical examinations. Safety assessments will be conducted according to the schedule presented in Table 6–1 for all age groups (2 to 12 years of age).

6.4.1 Adverse Events

6.4.1.1 Definitions of Adverse Events

The investigator is responsible for reporting all AEs that are observed or reported during the study, regardless of their relationship to study drug or severity. Each subject's LAR/caregiver will be instructed to contact the study center if the subject experiences any adverse events (AEs), is unable to take the study drug as prescribed, [REDACTED]

An AE is defined as any untoward medical occurrence in a subject enrolled into this study regardless of its causal relationship to study drug. Subjects will be instructed to contact the investigator at any time after enrollment if any symptoms develop.

Treatment-emergent AEs (TEAEs) are defined as AEs that start or increase in severity after the first dose of study drug in the study.

Situations where an untoward medical occurrence did not occur (social and/or convenience admission to a hospital) and anticipated day-to-day fluctuations of preexisting disease(s) or condition(s) present or detected at the start of the study that do not worsen are not AEs. Lack of drug effect is not an AE in clinical studies, because the purpose of the clinical study is to establish drug effect.

Cases of pregnancy that occur during maternal or paternal exposures to study drug are to be reported. Data on fetal outcome and breastfeeding are collected for regulatory reporting and drug safety evaluation.

Study site personnel will record the occurrence and nature of each subject's preexisting conditions, including clinically significant signs and symptoms of the disease under treatment in the study (e.g., seizures, motor dysfunction, sleep disruption, anxiety), as part of the medical history.

As seizures are often a baseline condition in subjects with AS, seizures should be reported as an AE in any of the following circumstances:

- There is a clear increase in the frequency of seizures compared to the subject's baseline.
- There is an emergence of a new seizure type.
- The subject experiences status epilepticus.

- The investigator believes the seizure should be captured as an AE (in which case the investigator should document his/her reasoning).

Seizures in this subject population will be detected and assessed using the seizure diary (Section 6.4.2.2). Diaries will be collected at the study site during the study and will be analyzed by the Sponsor along with the reportable SAEs in evaluating risks and benefits. The Sponsor will report the SAE events of seizure that meet these criteria in an aggregated, unblinded report at the end of the study.

After the informed consent form (ICF) is signed, site personnel will record any change in the condition(s) and the occurrence and nature of any AEs. If a subject experiences an AE after the ICF has been signed but before receiving study drug, the event will be reported and will be included in the subject's medical history unless the event is serious or the investigator feels the event may have been caused by a protocol procedure.

In addition, all AEs occurring after the subject receives the first dose of study drug must be reported to Ovid or its designee via the eCRF.

6.4.1.2 Serious Adverse Events

An SAE is defined as any event that

- Results in death.
- Is immediately life threatening.
- Requires inpatient hospitalization or prolongation of existing hospitalization.
- Results in persistent or significant disability/incapacity.
- Is a congenital anomaly or birth defect.

Important medical events that may not result in death, be life threatening, or require hospitalization may be considered SAEs when, based upon appropriate medical judgment, they may jeopardize the subject or may require medical or surgical intervention to prevent one of the outcomes listed in this definition. Examples of such medical events include allergic bronchospasm requiring intensive treatment in an emergency room or at home, blood dyscrasias or convulsions that do not result in inpatient hospitalization, or the development of drug dependency or drug abuse.

6.4.1.3 Eliciting and Documenting Adverse Events

Adverse events will be assessed beginning on the date of signed informed consent and up to 14 days after the last dose of study drug (unless a subject decides to participate in the ELARA open-label extension study) and must be followed until resolution or for 14 days after the subject's last study drug dose, whichever comes first.

Serious AEs that occur more than 30 days after the last dose of study drug need not be reported unless the investigator considers them related to study drug.

After informed consent is obtained, at every clinic visit and phone visit, subjects and their LAR/caregiver will be asked a standard nonleading question to elicit any medically-related changes in their well-being. They will also be asked if they have been hospitalized, had any accidents, used any new medications, or changed concomitant medication regimens (both prescription and over-the-counter medications).

In addition to subject observations, AEs identified from any study data (e.g., laboratory values, physical examination findings) or identified from the review of other documents (e.g., subject diaries) that are relevant to subject safety or considered to be clinically significant, in the medical and scientific judgment of the investigator, will be documented on the AE page in the eCRF.

6.4.1.4 Reporting Adverse Events

All AEs reported or observed during the study will be recorded on the AE page in the eCRF. Information to be collected includes the following:

- Drug treatment
- Dose
- Event term
- Time of onset
- Investigator-specified assessment of severity and relationship to study drug
- Time of resolution of the event
- Seriousness
- Any required treatment or evaluations

- Outcome

Adverse events resulting from concurrent illnesses, reactions to concurrent illnesses, reactions to concurrent medications, or progression of disease states must also be reported. All AEs will be followed to adequate resolution. The Medical Dictionary for Regulatory Activities (MedDRA) will be used to code all AEs.

Any medical condition that is present at the time the subject is screened and remains stable should not be reported as an AE. However, if the condition worsens at any time during the study, it should be recorded as an AE.

Any abnormal laboratory test results (hematology or clinical chemistry) or other safety assessments (e.g., vital sign measurements), including those that worsen from baseline, that are felt to be clinically significant in the medical and scientific judgment of the investigator are to be recorded as AEs.

6.4.1.5 Reporting Serious Adverse Events

All nonserious AEs must be recorded in the eCRF upon awareness.

Any AE that meets SAE criteria (Section 6.4.1.2) must immediately (i.e., within 1 business day) inform Ovid Drug Safety upon learning of any SAE that occurs (whether or not attributable to the study drug). It is the investigator's responsibility to ensure that SAE reporting procedures are followed appropriately. All SAE reports and any revisions to an SAE report must be sent to the email provided. All supporting source information concerning the SAE (e.g., hospital records) should also be provided by fax or email.

Country-specific fax numbers will be provided in a separate document.

Email: [contact]

If there is a question concerning an SAE, the site needs guidance regarding the reporting of an SAE, the site is returning a call from an Ovid Drug Safety specialist, the site urgently needs to report an SAE or make Ovid Drug Safety aware of an SAE, the safety hotline should be used (country-specific hotline numbers provided in a separate document).

If an SAE is reported via the hotline, the site should first submit the SAE paper form and then enter the SAE in the eCRF. Any AE that meets SAE criteria (Section 6.4.1.2) must be entered into the EDC system immediately (i.e., within 1 business day) after site personnel first learn about the event, in addition to faxing/emailing the SAE Report form. Once the qualifying SAE

data are entered into the EDC system, Ovid will be notified by an email alert, which will contain high-level safety information.

All SAEs must be reported starting from the time that informed consent for study participation is provided. If the investigator becomes aware of an SAE within 30 days after the subject's last dose of study drug or within 30 days after the last study visit, the SAE must be reported unless the patient has signed the consent to enroll into the ELARA open label extension study. Serious AEs must be followed until the event resolves, the event or sequelae stabilize, or it is unlikely that additional information can be obtained after demonstration of due diligence with follow-up efforts (i.e., the subject or health care practitioner is unable to provide additional information, or the subject is lost to follow-up). For subjects who do not sign the informed consent to enroll into the ELARA open label extension study, serious AEs that occur more than 30 days after the last dose of study drug should be submitted to the sponsor if the investigator becomes aware, however, these do not need to be reported to the IRB/EC or regulators unless the investigator or Sponsor considers them related to study drug.

6.4.1.6 Suspected Unexpected Serious Adverse Reactions and Nonserious Adverse Events of Special Interest

The Sponsor will promptly evaluate all suspected unexpected serious adverse reactions and nonserious AEs of special interest against cumulative product experience to identify and expeditiously communicate possible new safety findings to investigators, IRBs and IECs, and applicable health authorities based on applicable legislation.

To determine reporting requirements for single AE cases, the Sponsor will assess the expectedness of these events using the current OV101 investigator's brochure (Ovid Therapeutics Inc. 2018).

The Sponsor or its legal representative is responsible for notifying the relevant regulatory authorities of SAEs meeting the reporting criteria. This protocol will use Appendix 1 of the current investigator's brochure as the Reference Safety Document. The expectedness and reporting criteria of an SAE will be determined by the Sponsor from the Reference Safety Document.

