2.2.4 Safety Assessments

[figure not shown]
Adverse event (AE) occurrences will be recorded throughout the study. Adverse events will be assessed beginning on the date of signed informed consent and up to 14 days after the last dose of study drug (unless a subject decides to participate in the ELARA open-label extension study) and must be followed until resolution or for 14 days after the subject's last study drug dose, whichever comes first. If the investigator becomes aware of an SAE within 30 days after the subject's last dose of study drug or within 30 days after the last study visit or more than 30 days after the last dose of study drug if considered by the investigator to be related to study drug, the SAE must be reported.

Seizures in this subject population will be detected and assessed using the seizure diary. Diaries will be collected at the study site during the study and will be analyzed by the sponsor along with the reportable serious AEs (SAEs) in evaluating risks and benefits. The sponsor will report the SAE events of seizure that meet the criteria for reporting seizures as an AE (protocol section 6.4.1.1) in an aggregated, unblinded report at the end of the study.

Self-harm will be determined using the Aberrant Behavior Checklist – Irritability Subscale (ABC-I), which is one of the five subscales of the Aberrant Behavior

Checklist – Community (ABC-C). Additional safety assessments include clinical laboratory analyses, vital sign measurements, and physical examinations.

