3.9.1 Adverse Events

All adverse events will be coded using the MedDRA Version 22.0 and will be classified by MedDRA SOC and PT. Analyses of adverse events will be performed using the SS.

AEs that started on or after the first dose of study medication or worsened after the first dose of study medication through 14 days after the last dose of study medication and 30 days after the last dose of study drug/last study visit for SAEs are considered treatment-emergent AEs (TEAEs).

For all summaries, SOCs and PTs within SOC will be presented by decreasing frequency of incidence, sorted first for the OV101 group and then for the placebo group.

Handling of Missing or Partial Start Dates for Adverse Events

Rules for handling incomplete or missing adverse event start dates are addressed below (stop dates will not be imputed).

In the unusual case that the month portion of an adverse event start date is missing but the day portion is not missing, the day portion will be assumed to be missing.

Likewise, in the case where the year portion of an adverse event start date is missing but the month and/or day portion is not missing, the month and/or day portion will be assumed to be missing. All missing portion(s) of the date will be handled using the same rules:

- In the event that the day portion (and only the day portion) of the date is missing:
 - If the adverse event started in the same month and year as the first dose date, the adverse event start date will be assumed to be the first dose date.
 - Otherwise, the adverse event start date will be assumed to be the last day of the given month and year, e.g., XX–DEC-2005 would be 31-DEC-2005 where XX represents an unknown day.
- In the event that the day and month portions (and only the day and month portions) of the date are missing:
 - If the adverse event started in the same year as the first dose date, the adverse event start date will be assumed to be the first dose date.
 - Otherwise, the adverse event start date will be assumed to be last month and day of the given year, e.g., XX–XXX-2005 would be 31-DEC-2005 where XX represents an unknown day and XXX represents an unknown month.

- In the event that the day, month, and year portions of the adverse event start date are missing, it will be assumed to be the first dose date.

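### For children who roll into ELARA, the protocol and SAP draw the SAE boundary differently, and neither draws it by onset relative to the first ELARA dose

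*Protocol*

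**What the plan says.** **Protocol 6.4.1.5 (version 6.0).** The general duty is broad: "All SAEs must be reported starting from the time that informed consent for study participation is provided", and the sponsor's drug safety group must be told promptly "upon learning of any SAE that occurs (whether or not attributable to the study drug"). Section 6.4.1.1 adds that every AE after the first dose goes into the eCRF. For SAEs that the site learns of within 30 days of the last dose or last visit, a limit then applies: "the SAE must be reported unless the patient has signed the consent to enroll into the ELARA open label extension study".

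**SAP 2.2.4 and 3.9.1.** The collection rule begins "If the investigator becomes aware of an SAE within 30 days after the subject's last dose of study drug" and continues "or within 30 days after the last study visit or more than 30 days after the last dose of study drug if considered" related by the investigator. It has no ELARA exception for SAEs, although the preceding sentence has one for AE collection in general. Section 3.9.1 then classifies events up to 14 days after last dose and, for serious events, "30 days after the last dose of study drug/last study visit for SAEs are considered treatment-emergent AEs (TEAEs"). Neither window is cut at ELARA entry. The SAP Introduction ties the plan to protocol version 4.0.

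**Timing.** Protocol 3.1 makes the NEPTUNE end-of-treatment visit the ELARA baseline visit for children who roll over.

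**Late SAEs.** Protocol 6.4.1.3 says "Serious AEs that occur more than 30 days after the last dose of study drug need not be reported" unless the investigator thinks them related. Protocol 6.4.1.5 says that, for children without ELARA consent, such events "should be submitted to the sponsor if the investigator becomes aware".

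**The concern.** A handover between a blinded study and its open-label extension needs one line that both documents use, and onset relative to the first extension dose is the natural one because it separates the treatments. Here the protocol uses a consent signature combined with when the investigator became aware. The SAP uses elapsed days.

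Two errors are possible, in opposite directions. An SAE that began on blinded drug may be left out of NEPTUNE because the site heard of it after the ELARA signature. An SAE that began on open-label OV101 may be tabulated under the child's randomised arm, and for a placebo child that puts an event on active drug in the control column. Serious events are likely to be few. Section 1 of the protocol reports seizure SAEs in 2 subjects among 88 randomised in the Phase 2 study. With about 45 children per arm, one event moves an arm's SAE incidence by 1/45 = 2.2 percentage points.

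**Working it through.** The plan states no figure on this point, so there is nothing to reproduce. The check compares the texts, then illustrates the overlap.

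**Step 1. Apply each rule to a child who rolls over.**

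| SAE | Protocol 6.4.1.5 | SAP 2.2.4 and 3.9.1 |
|---|---|---|
| Began on blinded drug, learned of before ELARA consent | Reported in NEPTUNE | Collected and counted |
| Began on blinded drug, learned of after ELARA consent, within 30 days of last dose or visit | Exempt on the literal wording, but the general sentences still require it | Collected and counted |
| Began after first ELARA dose, within 30 days of last NEPTUNE dose or visit | Exempt | Within the collection rule, and counted as treatment-emergent if in the database |

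The documents disagree in rows 2 and 3. In row 2 the protocol is also in tension with itself, because it does not say how the exemption fits with the general duty. In row 3 the SAP gives no ground for excluding the event. Its Safety Set definition analyses by treatment actually received but has no rule for ELARA treatment, and the TEAE definition in Protocol 6.4.1.1 has no end date.

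**Step 2. Size of the overlap in the placebo arm.**

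Inputs from the documents: 45 placebo children (SAP 2.2.1); 12 weeks = 84 treatment days (synopsis); a 30-day SAE tail (SAP 3.9.1).

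Assumptions: 50% to 90% roll over at end of treatment, and ELARA dosing follows at once, so each contributes 30 open-label days.

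- Window per child from first dose: 84 + 30 = 114 days. For the arm: 45 x 114 = 5,130 child-days.
- Open-label days, low: 45 x 0.5 x 30 = 675. High: 45 x 0.9 x 30 = 1,215.
- Share of window: 675/5,130 = 13%; 1,215/5,130 = 24%. The ceiling, with everyone rolling over, is 30/114 = 26%.

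Dividing by the 45 x 84 = 3,780 treatment days gives 18-32%, but that leaves the tail out of the denominator while counting it in the numerator. The 13-24% is the consistent figure.

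**Step 3. Sensitivity to the start of ELARA.** The Pandemic Addendum asks for the Week 14 call before ELARA enrolment, whereas Section 3.1 places that visit in ELARA. If the Addendum is followed, about 30 - 14 = 16 open-label days remain, counting from last dose. The overlap is then 45 x 0.5 x 16 = 360 to 45 x 0.9 x 16 = 648 child-days, or 7-13% of the window.

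**Step 4. After a cut at the first ELARA dose.** The open-label days in the window fall to 0. Children who do not roll over keep their full 30 days.

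**The case against.** The strongest reply is that the protocol already prevents the second error. Once ELARA consent is signed, the site has no duty under this clause to report the event in NEPTUNE, and nothing in either document says that ELARA data are merged. SAP 3.9.1 classifies events; it does not collect them. This stands. A reader might infer that open-label SAEs will inflate the placebo rate, and the documents do not support that. It could happen only if a site enters such an event anyway, if a site follows the rule still written in SAP 2.2.4, or if data are pooled. What remains is that the SAP has no rule to exclude the event once it is there.

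On the first error, the general sentences in 6.4.1.1 and 6.4.1.5 still require reporting, and 6.4.1.3 has families asked about hospitalisation at every visit. The exposed case is therefore narrow: an SAE not disclosed by the end-of-treatment visit and learned of after signature. This also stands, and it makes the text ambiguous rather than a waiver. A reader might infer that such SAEs are lost to the sponsor. That cannot be shown, because the ELARA protocol is not among the documents and may capture them. The supportable risk is omission from the NEPTUNE tables.

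Two smaller points are also right. The SAP does not ignore ELARA altogether, since it has an exception for general AE collection. And the safety analyses are descriptive, so no formal test is affected.

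**Conclusion.** The point holds as a mismatch of stated rules. For rollover children the protocol draws the SAE line by consent signature and awareness, and the SAP draws it by 30 days from last dose or last study visit. Neither uses onset relative to the first ELARA dose, although end of treatment and ELARA baseline are the same visit. The consequences are possible omission of a late blinded-phase SAE from the NEPTUNE tables, and possible inclusion of an open-label SAE in a randomised arm.

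The 13-24% overlap rests on an assumed 50-90% rollover and immediate ELARA dosing. It describes exposure, not events, and it matters only for SAEs that reach the NEPTUNE database. The documents give no 30-day SAE rate from which to predict a count.

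The conflict between 6.4.1.3 and 6.4.1.5 on SAEs more than 30 days after the last dose is a separate wording problem and does not affect the arm comparison.

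**What to change.** 1. **Protocol 6.4.1.5:** state that any SAE with onset before the first ELARA dose is reported in NEPTUNE whenever it is learned of, regardless of ELARA consent.
2. **SAP 3.9.1:** end the TEAE window at the earlier of (a) 14 days after last dose, or for SAEs 30 days after last dose or last study visit, and (b) the time of the first ELARA dose. Say how an event on that calendar day without a clock time is assigned.
3. **SAP 2.2.4 and Introduction:** align with protocol version 6.0.
4. **Protocol 6.4.1.3 and 6.4.1.5:** reconcile the two statements on SAEs more than 30 days after last dose. Reconcile also the Pandemic Addendum and Section 3.1 on where the Week 14 visit takes place.

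The cost is a few clauses in each document and one added variable, the date and time of first ELARA dose, which should be available from the sponsor's own extension study. No visit, procedure or sample size changes.
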